9.2.6 Events of Clinical Interest for Group B HCC Subjects

Selected nonserious and serious adverse events are also known as ECIs and must be reported to the Sponsor.

Events of clinical interest for HCC subjects in this study include:

1. An overdose of Sponsor's product, as defined in Section 9.2.6.1, that is not associated with clinical symptoms or abnormal laboratory results.
2. Hepatic ECIs include any of the following events if the events are considered not due to disease progression as judged by the investigator. All of these events (if not associated with disease progression under study) will require holding study treatment, notification of the event(s) to the Sponsor within 24 hours after awareness via electronic media or paper.

For dose interval modification, refer to Section 6.2.2.2.1 and 6.2.2.2.2. For guidance related to the diagnosis and management of HECIs, refer to Section 9.2.5.1.

- ALT:
 - a. Among subjects with Baseline ALT < 2 x ULN: ALT ≥ 5 x ULN
 - b. Among subjects with Baseline ALT ≥ 2 x ULN: ALT > 3 x the Baseline level
 - c. ALT > 500 U/L regardless of baseline level
- Total Bilirubin:
 - a. Total bilirubin > 3.0 mg/dL
- Regardless of laboratory values, hepatic decompensation diagnosed clinically, including:
 - New onset clinically detectable ascites requiring intervention for > 3 days
 - Hepatic Encephalopathy
 - Gastrointestinal bleeding suggestive of portal hypertension (e.g., esophageal or gastric varices)

Progression of the cancer under study is not considered an ECI for pembrolizumab unless it is considered to be drug-related by the investigator.

9.2.6.1 Definition of an Overdose of Pembrolizumab for This Protocol and Reporting of Pembrolizumab Overdose

For this trial, an overdose of pembrolizumab will be defined as > 1000 mg (5 times the dose) of pembrolizumab. No specific information is available on the treatment of overdose of pembrolizumab. In the event of overdose, the subject should be observed closely for signs of toxicity. Appropriate supportive treatment should be provided if clinically indicated.

If an adverse event(s) or serious adverse event(s) is associated with (“result from”) the overdose of pembrolizumab, the adverse event(s) or serious adverse event is to be reported to Amgen as described in Sections 9.2.2 and 9.2.3, respectively. In addition, the adverse event(s) or serious adverse event(s) associated with (“result from”) the overdose of pembrolizumab should be reported as Event of Clinical Interest as described in Section 9.2.4.

9.3 Pregnancy and Lactation Reporting

If a female subject becomes pregnant, or a male subject fathers a child, while the subject is taking protocol-required therapies, report the pregnancy to Amgen Global Patient Safety as specified below.

In addition to reporting any pregnancies occurring during the study, investigators should report pregnancies that occur through 4 months after the last dose of talimogene laherparepvec or pembrolizumab, whichever is later (or 30 days following cessation of pembrolizumab if the subject initiates a new anticancer therapy, whichever is earlier).

The pregnancy should be reported to Amgen’s Global Patient Safety within 24 hours of the investigator’s awareness of the event of a pregnancy. Report a pregnancy on the Pregnancy Notification Forms ([Appendix C](#)). The Amgen’s Global Patient Safety will follow-up with the investigator regarding additional information that may be requested.

If a female subject becomes pregnant during the study, the investigator should attempt to obtain information regarding the birth outcome and health of the infant.

If the outcome of the pregnancy meets a criterion for immediate classification as a Serious Adverse Event (eg, female subject experiences a spontaneous abortion, stillbirth, neonatal death, or there is a fetal or neonatal congenital anomaly) the investigator will report the event as a Serious Adverse Event.

If a female breastfeeds while taking protocol-required therapies report the lactation case to Amgen Global Patient Safety as specified below.

In addition to reporting a lactation case during the study, investigators should monitor for lactation cases that occur after the last dose of protocol-required therapies through 4 months after the last dose of talimogene laherparepvec or pembrolizumab, whichever is later (or 30 days following cessation of pembrolizumab if the subject initiates a new anticancer therapy, whichever is earlier).

Any lactation case should be reported to Amgen's Global Patient Safety within 24 hours of the investigator's awareness of event. Report a lactation case on the Lactation Notification Worksheet ([Appendix C](#)). Amgen Global Patient Safety will follow-up with the investigator regarding additional information that may be requested.

If a male subject's female partner becomes pregnant, the investigator should discuss obtaining information regarding the birth outcome and health of the infant from the pregnant partner.

Pregnancies and lactations that occur after the consent form is signed but before enrollment must be reported by the investigator if they cause the subject to be excluded from the trial, or are the result of a protocol-specified intervention, including but not limited to washout or discontinuation of usual therapy, diet, or a procedure.

9.4 Reporting Exposure to Talimogene Laherparepvec

If a household member, caregiver, or healthcare provider who has had close contact with the subject is suspected to have been exposed to talimogene laherparepvec (eg, has signs or symptoms suspected to be herpetic in origin or is accidentally exposed to talimogene laherparepvec), while the subject is taking talimogene laherparepvec, report the exposure to Amgen as specified below. In addition to reporting an unintended exposure case during the study treatment, investigators should monitor for potential exposure cases that occur after the last dose of talimogene laherparepvec through 30 (+ 7) days after the last dose of talimogene laherparepvec.

Any potential or known unintended exposure should be reported to Amgen within 24 hours of the investigator's awareness of the event of exposure. Amgen will seek to follow-up with the exposed individual, if necessary, to collect more information about the exposed individual contact with clinical trial subject, signs and/or symptoms related to the exposure, medical history, and/or outcome of the exposure. If the exposed individual is reporting signs or symptoms suspected to be related to talimogene laherparepvec exposure, the exposed individual may be asked to have a swab taken from suspected lesions that are present to evaluate for the presence of talimogene laherparepvec DNA in the lesions by qPCR testing.

10. STATISTICAL CONSIDERATIONS

10.1 Study Endpoints, Analysis Sets, and Covariates

10.1.1 Study Endpoints

Primary Endpoint:

Part 1:

Monotherapy cohorts 1-4: Subject incidence of DLTs with intrahepatic injection of talimogene laherparepvec into liver tumors in subjects with non-HCC with liver metastases and subjects with HCC without active viral hepatitis.

Combination cohorts 5 and 6: Subject incidence of DLTs with intrahepatic injection into liver tumors of talimogene laherparepvec in combination with systemic IV administration of pembrolizumab in subjects with non-HCC with liver metastases and subjects with HCC with and without viral hepatitis.

Part 2:

- ORR per modified irRC-RECIST with intralesional injection of talimogene laherparepvec into cutaneous, subcutaneous, lymph node, and liver tumors in combination with systemic IV administration of pembrolizumab separately by tumor type arm (hormone receptor positive BC, TNBC, CRC, CSCC, BCC, and HCC with and without viral hepatitis)
- Subject incidence, for each tumor type arm, of treatment-emergent and treatment-related adverse events, including DLTs

Secondary Endpoint(s):

Efficacy:

Part 1:

- ORR, BOR, DRR, DOR, response in injected and uninjected lesions, DCR, PFS, and OS separately for non-HCC and HCC tumors in monotherapy and combination cohorts

Part 2:

- BOR, DRR, DOR, response in injected and uninjected lesions, DCR, PFS, and OS by primary tumor type arm (hormone receptor positive BC, TNBC, CSCC, CRC, BCC, and HCC with and without viral hepatitis)

Safety:

Parts 1 and 2:

- Subject incidence of treatment-related and treatment-emergent adverse events in each monotherapy and combination cohorts in Part 1 and each tumor type separately in Part 2, and HCC with and without viral hepatitis in Part 2
- Subject incidence of detectable talimogene laherparepvec DNA in blood and urine

- Incidence of clearance of talimogene laherparepvec DNA from blood and urine
- Subject incidence (per subject) and rate of detection (per sample) of talimogene laherparepvec DNA and virus at the surface of injection site, the exterior of the occlusive dressing, and the oral mucosa
- Subject incidence of talimogene laherparepvec DNA detection in lesions suspected to be herpetic in origin

Exploratory Endpoint:

10.1.2 Analysis Sets

DLT Analysis Set: The DLT analysis set will include DLT-evaluable subjects enrolled in Part 1 defined as follows:

- **Monotherapy Cohorts:** Subjects who have had the opportunity to be on treatment for at least 6 weeks from the initial dosing of study treatment and have received at least 1 additional dose of talimogene laherparepvec
- **Combination Cohorts:** Subjects who have had the opportunity to be on treatment for at least 6 weeks from the initial dosing of study treatment, and have received at least 2 doses of talimogene laherparepvec and pembrolizumab in combination
- **Subjects experiencing a DLT:** Have a DLT during the DLT-evaluation period after at least 1 dose of talimogene laherparepvec (for monotherapy cohorts) and talimogene laherparepvec and pembrolizumab (for combination cohorts)

Full Analysis Set: For efficacy analyses of talimogene laherparepvec monotherapy, the full analysis set will be defined as all subjects who received at least 1 dose of talimogene laherparepvec and no treatment with systemic pembrolizumab, and for efficacy analyses of talimogene laherparepvec in combination with systemic pembrolizumab, it will be defined as all subjects who received at least 1 dose of talimogene laherparepvec and at least 1 dose of pembrolizumab in combination.

Safety Analysis Set: The safety analysis set will be defined as all subjects who received study therapy. For monotherapy cohort, subjects will be included for analysis of safety if they received at least 1 dose of talimogene laherparepvec. For the combination therapy cohorts or part 2, subjects will be included for analysis of safety if they received at least 1 dose of talimogene laherparepvec or at least 1 dose of pembrolizumab.

Covariates and Subgroups

The following covariates may be used whenever applicable to examine efficacy and safety in subgroups or in multivariate analyses:

- Region, if applicable (USA vs non-USA)
- Age at baseline (< 50, ≥ 50; < 65, ≥ 65; < 75, ≥ 75 years)
- Baseline LDH (≤ ULN vs > ULN)
- Gender (Female vs Male)
- Baseline ECOG (0 vs 1)
- Baseline sum of lengths of measurable lesions
- Baseline sums of lengths of measurable liver lesions
- Prior exposure to chemo therapy (Yes vs No)
- HSV-1 serostatus (Yes vs No)
- Maximum talimogene laherparepvec volume at highest concentration per visit (≤ 4 mL vs > 4 mL)
- Baseline HBV or HCV status
- Baseline Microsatellite Instability status for CRC subjects

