dose tolerable. In Part 2, the DLRT may consider reducing the RP2D talimogene laherparepvec concentration and/or discontinuation of total volumes > 4 mL, if introduced. If the concentration is reduced in Part 2 for a tumor type arm, then the sample size considerations for the 2-stage futility and efficacy analyses of that tumor type arm will include only subjects treated at the reduced concentration. The DLRT can consider the totality of available clinical data when reviewing a given cohort.

3.1.4.1 Rules for DLT Evaluation and Dose Escalation for Part 1

Monotherapy Cohorts:

The DLT evaluation period for a given subject will consist of the period between the initial 10^6 PFU/mL dose of talimogene laherparepvec and 3 weeks following the initial 10^7 or 10^8 PFU/mL dose of talimogene laherparepvec. A subject will be considered to have had a DLT if they experience a DLT event (as outlined in Section 3.1.4.3) during the DLT evaluation period. Any subject who discontinues treatment or is lost to follow-up before the end of the DLT evaluation period for any reason other than DLT will not be considered evaluable for DLT and may need to be replaced by another subject in the same cohort.

Combination Cohorts:

The DLT evaluation period for a given subject will consist of the period between the initial 10^6 PFU/mL concentration of talimogene laherparepvec and 3 weeks following the initial 10^7 or 10^8 PFU/mL dose of talimogene laherparepvec. Any subject who has not received at least 2 doses of talimogene laherparepvec (10^6 , and 10^7 or 10^8 PFU/mL) and 2 doses of pembrolizumab, will not be considered DLT-evaluable unless they experience a DLT after the first dose. A subject will be considered to have had a DLT if they experience a DLT event (as outlined in Section 3.1.4.3) during the DLT evaluation period. Any subject who discontinues treatment, or is lost to follow-up before the end of the DLT evaluation period for any reason other than DLT, will not be considered evaluable for DLT and may need to be replaced by another subject in the same cohort.

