3.4 Replacement of Subjects

Subjects enrolled and treated may be replaced in Part 1 if they are not evaluable for DLT (eg, did not receive talimogene laherparepvec or ended study treatment before completion of DLT-evaluation period for a reason other than experiencing a DLT). Dose-limiting toxicity non-evaluable subjects will not be replaced in Part 2. The minimum and maximum number of DLT-evaluable subjects for a dose decision will be specified in the DLRT Charter.

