^d Includes Group B Cohort 6a and Cohort 6b

The first cycle of talimogene laherparepvec will be 21 (+3) days (from the first dose at 10^6 PFU/mL to the second dose at 10^7 or 10^8 PFU/mL). Subsequent cycles of talimogene laherparepvec will be 21 (± 3) days.

The maximum volume of talimogene laherparepvec administered at any dose is 4 mL (Cohorts 1, 2, 5, and 6) or 8 mL (Cohorts 3 and 4) for any individual lesion or for all lesions combined.

Part 2:

As of Protocol Amendment 6 (dated 26 October 2021), intrahepatic injections of talimogene laherparepvec and liver biopsies are no longer performed in this study.

In Part 2, talimogene laherparepvec can be administered into liver lesions, lymph nodes, cutaneous or subcutaneous tumors (non-hepatic lesions). It is mandatory that administration into liver lesions is by image guided injection (either by US or CT scan). Image guidance may also be used for other non-hepatic intratumoral injections but is not required if the lesion is easily visible or palpable. The concentration of talimogene laherparepvec (10^7 or 10^8 PFU/mL) to be administered in Part 2 will be determined on completion of the combination treatment, Cohorts 5 and 6, in Part 1. Talimogene laherparepvec will be used at a maximum volume of 8 mL (established from monotherapy Cohort 3 in Part 1). No intrasubject concentration or volume escalation is allowed. Investigators are encouraged to use the maximum amount whenever lesions allow. Dose reduction for adverse events is not allowed. However, if in the course of administration of talimogene laherparepvec the subject cannot tolerate the full volume due to an injection-related adverse event such as pain, the total volume given should be recorded, and the reason for intolerance should be documented as an adverse event.

The recommended volume of talimogene laherparepvec to be injected into the tumor(s) depends on the longest diameters of the tumor(s) and necrotic core of the tumor(s) (if applicable) and should be dosed according to the injection volume guideline in [Table 3](#).

Liver Lesions with Necrotic Cores

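### The DLT Analysis Set can include subjects who left after dose 2 but before the DLT window closed, whom Protocol Section 3.1.4.1 calls not evaluable, so the reported DLT incidence can fall below the rate behind the dose decision

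*Protocol*

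**What the plan says.** Two definitions of a DLT-evaluable subject are in force.

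- **Protocol Section 3.1.4.1 (Part 1 rules).** For monotherapy, the window is the "period between the initial 10^6 PFU/mL dose of talimogene laherparepvec and 3 weeks following the initial 10^7 or 10^8 PFU/mL dose". Someone who stops treatment or is lost "before the end of the DLT evaluation period for any reason other than DLT will not be considered evaluable for DLT". The combination cohorts have the same window and the same exclusion, plus a requirement for two doses of each drug.
- **Protocol Section 3.4** uses the same idea to decide who may be replaced in Part 1, giving as an example a subject who "ended study treatment before completion of DLT-evaluation period for a reason other than experiencing a DLT". Protocol Section 10.2 and SAP 3.2 repeat it for monotherapy.
- **Protocol Section 10.1.2** gives its own definition: "Subjects who have had the opportunity to be on treatment for at least 6 weeks from the initial dosing of study treatment", who in monotherapy "have received at least 1 additional dose of talimogene laherparepvec" and in combination "have received at least 2 doses of talimogene laherparepvec and pembrolizumab in combination". A subject with a DLT inside the window also qualifies. Completing the window is not required.
- **SAP 6.3** repeats these criteria and extends the set to Part 2. SAP Section 5 restates the window and the combination dose-count rule but not the early-leaver exclusion.

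Protocol Section 10.4.1 and SAP 9.6.1 (Table 9-4) make this set the denominator of the Part 1 primary endpoint, subject incidence of DLT. Protocol Section 10.2 and SAP 9.6.1 also use it for DLT incidence in Part 2.

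**The concern.** Opportunity means potential follow-up, not completed follow-up. A programmer working from SAP 6.3 would keep a subject who took dose 2 and left a few days later, and would count that subject as DLT-free. The same subject is not evaluable under the rule that governs escalation and replacement.

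At stake is whether the reported primary safety result agrees with the decision it should document. Monotherapy cohorts have 3 to 6 evaluable subjects, so one extra DLT-free subject shows. A cohort declared not safe on 2 DLTs in 6 could appear in the report at a rate below the 1/3 limit in Section 3.1.4.1, with no explanation.

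**Working it through.** **1. Length of the window.** Section 6.2.1.1 states "The first cycle of talimogene laherparepvec will be 21 (+3) days", so dose 2 is scheduled for day 21 to 24 after dose 1. Adding 3 weeks gives 21 + 21 = 42 days to 24 + 21 = 45 days. The analysis set asks for 6 weeks, which is 42 days, so its time criterion can fall up to 3 days short of the window even for subjects who stay.

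**2. Who is classified differently.** For subjects without a DLT:

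| Subject | Section 3.1.4.1 | Section 10.1.2 and SAP 6.3 |
|---|---|---|
| Leaves before dose 2 (of either drug in combination) | not evaluable | not in the set |
| Leaves after dose 2, before the window ends | not evaluable | in the set, DLT-free |
| Completes the window with the required doses | evaluable | in the set |

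Only the middle row conflicts.

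**3. The plan's own figure.** Table 16 gives the probability of declaring a monotherapy cohort safe. Under 3+3, P(safe) = (1−p)³ + 3p(1−p)² × (1−p)³. For p = 0.1, 0.2, 0.3, 0.4 and 0.5 this gives 0.906, 0.709, 0.494, 0.309 and 0.172. Table 16 prints 0.91, 0.71, 0.49, 0.31 and 0.17, so it reproduces. The formula treats every counted subject as fully observed, which matches Section 3.1.4.1 and not Section 10.1.2.

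**4. Reported incidence against the decision denominator.** With x DLTs, n evaluable subjects and k early leavers kept, x/n becomes x/(n+k). For k = 1:

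- 2/6 = 33.3% becomes 2/7 = 28.6%
- 4/6 = 66.7% becomes 4/7 = 57.1%
- 5/12 = 41.7% becomes 5/13 = 38.5%

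The added subjects have no DLT by construction, so the change is always downward.

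**5. Reported incidence against the true rate.** This needs two quantities that the documents do not give: d, the share of counted subjects who leave early, and q, the share of their DLT risk that goes unobserved. The expected observed rate is p(1 − dq). For p = 40%:

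- d = 5%, q = 0.5: 40% × 0.975 = 39.0%
- d = 20%, q = 1: 40% × 0.80 = 32.0%
- q = 0 (leavers fully observed): 40%, no dilution

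The values of d and q are assumptions. Step 4 is arithmetic for a given count of leavers. Step 5 depends on how completely they were followed.

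**The case against.** The case against is substantial, and several parts of it stand.

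- **Stopping treatment is not the same as leaving observation.** Both drugs are given every 3 weeks, so no further dose is scheduled between dose 2 and about the end of the window. Section 6.2.1.2 keeps subjects who discontinue talimogene laherparepvec in study procedures, including the 30-day safety visit. Section 9.2.2 collects adverse events for 30 (+7) days after the last dose, longer than the 21 days left after dose 2. For these subjects q may be near zero. Real under-observation arises mainly with loss to follow-up or withdrawal of consent.
- **Toxicity-driven leavers are largely caught.** Related intolerable toxicity that leads to permanent discontinuation is itself a DLT under Section 3.1.4.3, as is related death.
- **The result is descriptive.** Formal analysis is reserved for the Part 2 primary endpoints.
- **The SAP is not silent.** SAP 3.2 states the exclusion as a replacement rule for monotherapy cohorts.

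These points limit the bias but do not remove the contradiction. The set's lead-in mentions DLT-evaluable subjects, but the text then supplies its own criteria, so Section 3.1.4.1 is not carried in.

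A reader might go further and infer that dose decisions were wrong. In Table 17 one extra DLT-free subject moves 3/4 (de-escalate) to 3/5 (stay). Under the assumed ranges in step 5, P(safe) at a true 40% would rise from 0.31 to between 0.33 and 0.45. The documents do not support that inference. The 3+3 rule counts DLTs among evaluable subjects, the Table 17 footnote refers to DLT-evaluable subjects, and the operating detail is in a DLRT Charter that is not available here. These shifts arise only if the DLRT counted by the Section 10.1.2 set.

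**Conclusion.** The contradiction is real and narrow. It covers only subjects without a DLT who left after dose 2 (of both drugs in combination cohorts) and before the window ended. If any exist, the reported DLT incidence is lower than the rate under the protocol's own evaluability rule. The gap is about 5 percentage points for one such subject added to 2/6 (33.3% to 28.6%) and about 3 for one added to 5/12 (41.7% to 38.5%).

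It would go too far to say that the denominator is in fact inflated, or that all early leavers are kept. The documents give no count of affected subjects, and those who left before dose 2 without a DLT are out under both definitions. Nor is the reported rate shown to be biased against the truth, since that depends on follow-up after leaving. What is established is that the SAP as written can produce a primary DLT incidence inconsistent with the rate behind the dose decision. It should be corrected before the DLT tables are final.

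**What to change.** Reconcile Protocol Section 10.1.2, SAP 6.3 and SAP Section 5 with Section 3.1.4.1:

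- Define the DLT Analysis Set as subjects with the required doses who are evaluable under Section 3.1.4.1 through the end of the DLT evaluation period, or who had a DLT within it.
- Tie the time criterion to the end of that period, which can run to 45 days, instead of a fixed 6 weeks.
- State which date marks discontinuation. SAP Section 5 defines both a last dose date and a date on which the decision to end treatment was made, and the two classify these subjects differently.
- Say whether the same rule applies to DLT incidence in Part 2, since Section 3.1.4.1 is headed for Part 1 and SAP 6.3 covers both parts.
- Use this denominator in all DLT incidence tables, and list the subjects excluded for leaving after dose 2, so that a reader can see what counting them would do.

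The cost is a short change to the set definition and one listing. Enrollment has stopped, and no new data are needed. The downside is a slightly smaller denominator if such subjects exist, some of whom may have been adequately observed. The listing keeps them visible.
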